### 12.4.3 Analysis of Exploratory Endpoints

Duration of Response (DOR) will be analyzed by Kaplan-Meier descriptive statistics for patients who have a response of sCR, CR, VGPR or PR, as assessed by IMWG criteria. DOR will be calculated as the number of days from the date of the first evidence of response until progression or death. Patients who have not progressed at the time of analysis will be censored at the last available assessment date at which no evidence of disease was observed. Estimates will include the 25th, 50th (median), and 75th percentiles and associated 95% CIs, as well as the number and percentage of censored patients.

The clinical benefit rate (CBR) will be performed by calculating the point estimate of the percentage of patients who have a response of sCR, CR, VGPR, PR or MR, as assessed by IMWG criteria. Analysis will be performed by calculation of the point estimate of CBR, as well as a two-sided 95% CI, using exact methods.

The disease control rate (DCR) will be performed by calculating the point estimate of the percentage of patients who have a response of sCR, CR, VGPR, PR, MR or SD, as assessed by IMWG criteria. Analysis will be performed by calculation of the point estimate of DCR, as well as a two-sided 95% CI, using exact methods.

Progression-free Survival (PFS) will be calculated from the date of start of study therapy to the date of progression based on IMWG criteria, or date of death due to any cause should progression not have occurred. Patients who drop out prior to study end will be censored at the last available assessment date at which no evidence of disease was observed. The analysis of PFS will be based on the Kaplan-Meier method for estimation of summary statistics, and include the 25th, 50th (median), and 75th percentiles and associated 95% CIs.

Overall Survival (OS) will be calculated from the date of start of study therapy to the date of death due to any cause. This analysis will be performed in the same manner as the analysis of PFS.

Patients will be provided medication diaries at the beginning of each cycle. Delivered dose intensity will be assessed on day 1 of each cycle starting on cycle 2; defined as the total amount of study drug taken in one cycle.

The standard dose intensity is defined as the cumulative planned dose for cycle 1.

The relative dose intensity (RDI) is calculated by dividing the average delivered dose intensity over the standard dose intensity, expressed as a percentage.

Quality of life (QOL) will be assessed by completing the Functional Assessment of Cancer Therapy - MM (FACT-MM) (Appendix 5) questionnaire as outlined in Table 2. The FACT-MM questionnaire consists of the four core FACT HRQoL subscales measuring physical, functional, social, and emotional well-being (FACT-G; 27 items) and an additional subscale (MM subscale) measuring MM-specific concerns (14 items). Items are rated using a 0- to 4-point scale based on the past 7 days, with higher scores indicating better HRQoL and fewer MM-related symptoms. The actual value and change from baseline of each subscale and total score will be summarized for all study patients

combined. By-patient listings of each subscale and total score will be presented in data listings.

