### **1.2.3 Exploratory Objectives**

- To determine the duration of response of combination therapy with ClaSPd for the treatment of patients with RRMM.
- To determine the time to maximum response of combination therapy with ClaSPd for the treatment of patients with RRMM.
- To determine the clinical benefit rate of combination therapy with ClaSPd for the treatment of patients with RRMM.
- To determine the disease control rate of combination therapy with ClaSPd for the treatment of patients with RRMM.
- To determine the progression-free survival of combination therapy with ClaSPd for the treatment of patients with RRMM.
- To determine the overall survival of combination therapy with ClaSPd for the treatment of patients with RRMM.
- To determine the relative dose intensity of combination therapy with ClaSPd for the treatment of patients with RRMM.
- To assess quality of life during combination therapy with ClaSPd for the treatment of patients with RRMM.

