## **10.2 Duration of Response**

Duration of response: The duration of response is measured from the time measurement criteria for PR, VGPR, CR or sCR (whichever is first recorded) is first met until the date of progressive disease (PD) or death, whichever comes first.

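### The duration-of-response censoring sentence in Section 12.4.3 conflicts with the definition just before it: read literally, it censors responders who die without progression

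*Combined protocol and SAP*

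**What the plan says.** Three statements in the combined protocol and SAP bear on when a response ends.

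- Section 10.2 runs DOR from the first recorded response "until the date of progressive disease (PD) or death, whichever comes first".
- Section 12.4.3 repeats this: "DOR will be calculated as the number of days from the date of the first evidence of response until progression or death".
- The next sentence of 12.4.3 is the only censoring rule for DOR: "Patients who have not progressed at the time of analysis will be censored". It sets the censoring date at the latest assessment that showed the patient free of disease.

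The method is descriptive Kaplan-Meier in responders only: "Duration of Response (DOR) will be analyzed by Kaplan-Meier descriptive statistics for patients who have a response of sCR, CR, VGPR or PR". DOR is listed as an exploratory objective in Section 1.2.3.

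The PFS paragraph of 12.4.3 is worded differently. Its event is progression, "or date of death due to any cause should progression not have occurred", and its censoring clause is tied to leaving the study: "Patients who drop out prior to study end will be censored".

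**The concern.** A responder who dies without progression has, in plain words, not progressed. The two definitions make that patient an event on the date of death. The censoring sentence, taken alone, makes the same patient a censored observation at an earlier assessment. A programmer working from 12.4.3 could follow either sentence, and the different PFS wording could be taken as a sign that the difference is deliberate.

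At stake is what the reported DOR means. With deaths censored, the Kaplan-Meier curve estimates time to progression among responders as if nobody died first, so a fatal toxicity during response would not shorten it. DOR and PFS would then treat death differently in the same report. Durability of response is part of the rationale in Sections 2.3 and 2.4.3, so the figure will be read.

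The sentence has a second fault. It places censoring at an assessment with no evidence of disease. Under Appendix 4, a partial response needs only a 50% fall in serum M-protein (with the urine criterion), and a very good partial response can leave M-protein detectable by immunofixation. Such responders may never have an assessment of the kind the rule asks for.

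**Working it through.** **Plan's own figure.** The plan states no expected DOR and no share of deaths in response, so there is no figure to reproduce. The check is a comparison of texts, followed by an illustration under stated assumptions.

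**Step 1. Apply each sentence to each type of responder.**

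| Responder at analysis | Definition (10.2; 12.4.3) | Censoring sentence (12.4.3), literal |
|---|---|---|
| Progressed | Event | Not censored |
| Alive, not progressed | No event | Censored |
| Died without progression | Event on date of death | Censored at last qualifying assessment |

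Only the third row conflicts.

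**Step 2. Size under constant hazards.** Let m be the true median with deaths counted as events, and f the share of DOR events that are deaths without progression. The total hazard is ln 2 / m and the progression hazard is (1−f) × ln 2 / m. Censoring deaths leaves only the progression hazard, so the median becomes m/(1−f). With m = 10 months (assumed):

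- f = 5%: 10/0.95 = 10.5 months
- f = 10%: 10/0.90 = 11.1 months
- f = 20%: 10/0.80 = 12.5 months

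The 12-month DOR is 0.5^1.2 = 43.5% with deaths as events, and 0.5^(1.2(1−f)) with deaths censored:

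- f = 5%: 45.4%, up 1.8 points before rounding
- f = 10%: 47.3%, up 3.8 points
- f = 20%: 51.4%, up 7.9 points

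**Step 3. Compare with sampling error.** At the 60% response rate of the alternative hypothesis (Section 12.1), 26 × 0.60 = 15.6, or about 16 responders. Ignoring censoring, the standard error of the 12-month estimate is about √(0.435 × 0.565 / 16) = 0.124, or 12 points. Half of that, about 6 points, is reached at f of about 15% to 16%: at 15%, 0.5^1.02 = 49.3%, up 5.8 points.

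**Step 4. Small-sample check.** In 4,000 simulated trials per value of f (16 responders, true median 10 months, administrative censoring uniform on 12 to 25 months), the typical Kaplan-Meier median was 9.1 to 9.2 months with deaths as events. With deaths censored at the time of death it was 9.9, 10.6 and 12.3 months for f = 5%, 10% and 20%. The mean number of deaths reclassified per trial was 0.6, 1.2 and 2.3.

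**Step 5. Direction in a single sample.** Steps 2 and 4 censor at the time of death, but the literal rule censors earlier, at the last qualifying assessment. Take two responders: A is last assessed at month 4 and dies at month 5; B progresses at month 4.5. With death as an event, both are at risk at 4.5, so S(4.5) = 1/2. Under the literal rule A leaves the risk set at month 4, so S(4.5) = 0. The bias is therefore upward on average, not in every dataset.

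**The case against.** The strongest reply is that the text already settles the matter. Death is named as a DOR event twice, the second time in the sentence directly before the censoring rule. A responder who dies already has an end date, so the natural reading is that the next sentence covers only patients with no event. Nothing gives the censoring sentence priority. This stands, and it rules out the stronger reading that a reader might infer: that the plan has decided to censor deaths and so overstates DOR. The fault is a loosely worded sentence at odds with its own definition.

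The contrast with PFS is also weaker than it looks. The PFS sentence censors patients who drop out and, read as strictly, gives no rule for someone still on study without progression. Both sentences are shorthand, so a deliberate difference between them is not shown.

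A reader might also infer from the background that deaths in response will be common. The documents do not support that. The excess treatment-related deaths with clarithromycin in the phase 3 trial (Sections 2.2.2 and 2.4.1.5) fell mainly on patients aged 75 or older with newly diagnosed disease, and Section 4.2 requires age under 75. Of the three fatal events with selinexor, pomalidomide and dexamethasone (Section 2.4.1.4), two came in cycles 1 and 2, and the patient with fatal pneumonia in cycle 5 is not said to have been in response.

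Finally, 12.4.3 requires the number and percentage of censored patients, and 12.4.2 a by-patient listing of deaths, so a reclassified death could be traced. That limits the harm, but it does not tell the programmer which sentence to follow.

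**Conclusion.** The conflict is real, and nothing else in the document resolves it. Applied as written, the censoring sentence gives a result that contradicts the plan's own definition of DOR, and its censoring date does not fit responders with residual M-protein.

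The consequence is conditional. If the sentence is programmed literally, DOR is biased upward on average, with the median multiplied by 1/(1−f) under constant hazards. Both the 10-month median and f are assumptions. At f of 5% to 10% the 12-month estimate moves by 1.8 to 3.8 points, against a standard error of about 12. The claims that DOR is overstated as the plan stands, or that any error must be upward, go further than the text and the arithmetic allow.

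DOR is exploratory and descriptive. The test of the response rate, the sample size and the two-stage stopping rule (Sections 12.1, 12.2 and 12.5) do not use it. This is a minor correction.

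**What to change.** Replace the DOR censoring sentence in 12.4.3 with:

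> Responders who have neither progressed nor died at the time of analysis will be censored at their last disease assessment showing no progression; death without prior progression is an event on the date of death.

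This brings the rule into line with both definitions and gives partial and very good partial responders a censoring date they can have. The PFS censoring sentence ends with the same reference to absence of disease and could take the same change of date.

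The cost is one sentence. The downside is that the reported median DOR may be slightly shorter than under the literal rule. The change should be made before the DOR data are examined, so that the handling of deaths is not chosen after they are known.

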	Grade 3 or 4	
Delay selinexor until resolved to Grade 1, then reduce selinexor dose by 1 dose level.
 
If diarrhea stabilizes for at least 4 weeks at Grade <math>\leq</math> 1, may re-escalate to previous dose of selinexor after consulting with the Medical Monitor.

Thrombocytopenia	Grade 1	Maintain dose.
	Grade 2 or 3 without bleeding	
Consider platelet growth factors, e.g., romiplostim, which may take up to four weeks for an effect.
 
Reduce selinexor at 1 dose level lower.
 
Patients with stable platelet counts for <math>\geq</math> 4 weeks following dose reduction may have their dose of selinexor increased by one dose level.

	Grade 4 without bleeding	Strongly consider platelet growth factors and transfuse per clinical practice/institutional guidelines. Delay dosing until recovery to $\leq$ Grade 2 or baseline and resume selinexor at 1 dose level lower.
	Grade 2 or 3 with bleeding	Delay dosing until the bleeding has stopped and the patient is clinically stable. Reduce selinexor at 1 dose level lower.
Neutropenia	Grade 3 or 4 Neutropenia without fever	Institute colony stimulating factors, and delay dosing with selinexor until ANC returns to Grade $\leq$ 2. Reduce selinexor by 1 dose level. After stabilization for at least 4 weeks, a re-escalation may be considered after discussing with the Medical Monitor.
	Grade 3 or 4 Neutropenia with fever	Institute colony stimulating factors, and delay dosing with selinexor until the patient's ANC returns to Grade $\leq$ 2 or baseline, fever has resolved, and patient's condition is stable. Reduce selinexor by 1 dose level.
Anemia	Grade 3	Treat per institutional guidelines including blood transfusions and/or erythropoietins. Consider transfusing for Hb $<$ 8 g/dL. Reduce selinexor by 1 dose level.
	Grade 4	Treat per institutional guidelines including blood transfusions and/or erythropoietins. Consider transfusing for Hb $<$ 8 g/dL. Delay dosing of selinexor until Hb is 8 g/dL or higher. Reduce selinexor by 1 dose level.
Ocular Toxicity	Grade 2, excluding cataract	Perform ophthalmologic evaluation. Interrupt selinexor and provide supportive care. Monitor until ocular symptoms resolve to Grade 1 or baseline. Restart selinexor at 1 dose level lower.
	Grade 3 or 4, excluding cataract	Permanently discontinue selinexor. Perform ophthalmologic evaluation.

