Other Selinexor-related AEs	Grade 1 or 2	Maintain dose. Initiate standard supportive care per institutional guidelines.
	Grade 3	Delay dosing with selinexor until recovery to Grade $\leq$ 2 or baseline and resume selinexor at 1 dose level lower. Re-escalation can be considered after $\geq$ 4 weeks at the lower dose with reduction of the AE to Grade 1 or baseline.
	Grade 4	Delay dosing until resolved to Grade $\leq$ 2 or baseline, then resume at 1 dose level lower. If further dose reduction/interruption is desired, consultation with the Medical Monitor is required.
Clarithromycin		
Nausea and/or Vomiting	Grade 1 or 2	Maintain dose. Rule out other causes of nausea. Patients should be receiving 5HT3 antagonists unless contra-indicated. For those patients who cannot receive 5HT3 antagonists, consider olanzapine per NCCN CPGO. For additional options, see NCCN CPGO.

		If intolerable or persistent Grade 2, follow guidelines for Grade 3.
	Grade $\geq 3$	
Supportive care medications per institutional guidelines should already be instituted. For additional options see NCCN CPGO.
 
If AE is thought to be due to clarithromycin, interrupt clarithromycin dosing until resolved to Grade <math>\leq 2</math> or baseline. For first occurrence of Grade 3, if adequate supportive care resulted in an improvement to Grade 1 or baseline within 3 days, restart clarithromycin at current dose.
 
Otherwise (i.e., the recovery took longer than 3 days), restart clarithromycin at 1 dose level lower.
 
If nausea stabilizes for at least 4 weeks at Grade <math>\leq 1</math>, may re-escalate to the original dose after consulting Medical Monitor.

Other Clarithromycin-related Non-hematologic AEs	Grade $\geq 3$	Hold (interrupt) clarithromycin and follow weekly. If toxicity has resolved to Grade $\leq 1$ , restart clarithromycin at next lower dose level.
Dexamethasone		
Dyspepsia, Gastritis, Gastric or Duodenal Ulcer	Grade $\geq 3$	Hold (interrupt) dexamethasone and follow weekly. If toxicity has resolved to Grade $\leq 1$ , restart dexamethasone at next lower dose level.
Edema	Grade $\geq 3$	Reduce the dose of dexamethasone by 1 dose level. Use diuretics as needed.
Agitation, Confusion, and/or other Psychiatric Disorder	Grade $\geq 2$	Hold (interrupt) dexamethasone and follow weekly. If toxicity has resolved to Grade $\leq 1$ , restart dexamethasone at next lower dose level.

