#### **7.8.14 Instructions for initiation of a subsequent cycle**

A new course of treatment may begin on the scheduled day 1 of a new cycle if:

- Absolute neutrophil count (ANC)  $\geq$  1,000 cells/mm^3
- Platelets count  $\geq$  75,000/mm^3
- Any drug-related somnolence, rash, peripheral neuropathy, sinus bradycardia/other cardiac arrhythmia, allergic reaction/hypersensitivity, dyspepsia, gastritis, gastric or duodenal ulcer or confusion or mood alterations that may have occurred has resolved to  $\leq$  grade 1 severity.
- Any other drug-related non-hematologic adverse events that may have occurred have resolved to  $\leq$  grade 2 severity.

If these conditions are not met on Day 1 of a new cycle, the subject will be evaluated weekly and a new cycle of treatment will not be initiated until the toxicity has resolved as described above.

If the toxicity does not resolve within four weeks, the patient will be taken off the study. If the dosing of selinexor, clarithromycin, pomalidomide or dexamethasone was halted during the previous cycle and was restarted with a one-level dose reduction without

requiring an interruption for the remainder of the cycle, then that reduced dose level will be initiated on day 1 of the new cycle.

If the dosing of selinexor, clarithromycin, pomalidomide or dexamethasone was omitted for the remainder of the previous cycle or if the new cycle is delayed due to toxicity newly encountered on the scheduled day 1, then the new cycle will be started with dose modifications as described in Tables 3 and 4.

If the start of a new cycle is delayed more than 4 weeks, the patient will be taken off study.

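### Relative dose intensity in 12.4.3 has no elapsed-time term, so a cycle start delayed by up to 4 weeks does not itself lower it

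*Combined protocol and SAP*

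**What the plan says.** Section 12.4.3 builds RDI in three steps. Delivered dose intensity, read from the medication diaries on day 1 of each cycle from cycle 2, is "defined as the total amount of study drug taken in one cycle". The reference is fixed: "The standard dose intensity is defined as the cumulative planned dose for cycle 1". RDI is then obtained by "dividing the average delivered dose intensity over the standard dose intensity, expressed as a percentage". Section 10.4 describes the same measure as delivered over planned dose intensity and gives no time unit.

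Section 7.8.14 governs cycle starts. If the conditions for a new cycle are not met on day 1, the patient is checked weekly and "a new cycle of treatment will not be initiated until the toxicity has resolved as described above". The limit is: "If the start of a new cycle is delayed more than 4 weeks, the patient will be taken off study". Where a drug was omitted for the rest of the previous cycle, or the delay is due to toxicity newly found on the scheduled day 1, "then the new cycle will be started with dose modifications as described in Tables 3 and 4".

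Table 4 sets those modifications drug by drug. For Grade 3 or 4 neutropenia the selinexor entry says "Reduce selinexor by 1 dose level". Clarithromycin and dexamethasone have entries only for non-haematologic events; the general clarithromycin row, for example, is "Other Clarithromycin-related Non-hematologic AEs". Section 7.7.1 requires every dose modification and treatment delay to be documented with its reason.

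**The concern.** Dose intensity is normally read as dose per unit of time. Here both numerator and denominator are mg per cycle, and a cycle can be followed by a hold of up to 4 weeks before the next one starts. Assigning the hold to the preceding cycle changes nothing, because the numerator is still total mg. RDI therefore responds to dose reductions and to doses omitted within a cycle, but not to lateness between cycles.

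The error runs in one direction: late cycles can only make delivery look better than it was. RDI is one of eight exploratory objectives in 1.2.3 and the only one that says how much of the four-drug regimen patients received. At stake is an RDI near 100% reported alongside real gaps in treatment.

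**Working it through.** The plan states no RDI value, so there is no figure to reproduce. The check applies the 12.4.3 formula and a per-time version to the same dosing histories.

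**Inputs.** Planned dose per 28-day cycle (section 7.7):
- selinexor 60 × 3 = 180 mg
- clarithromycin 500 × 2 × 28 = 28,000 mg
- pomalidomide 4 × 21 = 84 mg
- dexamethasone 40 × 4 = 160 mg

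Selinexor level -1 is 40 × 3 = 120 mg (Table 3). The longest permitted delay of a cycle start is 28 days (7.8.14). Assumption: no study drug is taken during a hold between cycles.

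**Formulas.**
- Plan: RDI = mean mg per cycle / planned cycle 1 mg × 100.
- Per time: RDI = (total mg / actual weeks) / (planned cycle 1 mg / 4 weeks) × 100.

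For a drug taken in full throughout, the second reduces to planned days / (planned days + days of delay).

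**Two full-dose cycles, second start delayed.** The plan's formula gives 100% in each case. Per time:
- 7 days: 56/63 = 88.9%
- 14 days: 56/70 = 80.0%
- 28 days: 56/84 = 66.7%

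**Ten full-dose cycles.** Ten cycles are 280 days, close to the roughly 10 months of treatment expected in the Protocol Summary. With k of the nine later starts delayed, the plan's formula gives 100% throughout. Per time:

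| Delayed starts k | 7 days each: 280/(280 + 7k) | 14 days each: 280/(280 + 14k) |
|---|---|---|
| 1 | 97.6% | 95.2% |
| 3 | 93.0% | 87.0% |
| 5 | 88.9% | 80.0% |
| 9 | 81.6% | 69.0% |

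**Selinexor reduced to level -1 from cycle 2, ten cycles.** Total mg = 180 + 9 × 120 = 1,260. Plan's formula: 1,260/1,800 = 70.0%. Per time, against 180/4 = 45 mg per week:
- 7 days of total delay: (1,260/41)/45 = 68.3%
- 14 days: (1,260/42)/45 = 66.7%
- 28 days: (1,260/44)/45 = 63.6%

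The omitted delay is therefore worth 70.0 − 68.3 = 1.7 to 70.0 − 63.6 = 6.4 points once the dose has been cut.

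**Which drugs stay at full dose.** In a blood-count delay Table 4 lists no reduction for clarithromycin or dexamethasone. Pomalidomide can also stay at full dose, since Table 4 maintains it for Grade 3 neutropenia without fever. Selinexor will usually be reduced, so the last calculation is the relevant one for it.

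**The case against.** The strongest reply is that 12.4.3 is explicit and reproducible, 10.4 names no time unit, and the two do not conflict. Dose taken per cycle against dose planned is a coherent measure that captures reductions and omitted doses. Nothing in the documents says intensity must be per week. This stands in part: the definition is neither ambiguous nor contradictory. But the measure is called dose intensity, the protocol expressly permits holds between cycles, and no other section brings the lost time in, so the result overstates intensity whenever a cycle starts late.

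Three further limits stand.

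- A reader might infer larger gaps by setting one cycle against that cycle plus its delay: 28/35 = 80.0%, 28/42 = 66.7%, 28/56 = 50.0%. Those figures apply only if treatment stops for good when the hold ends. A delayed start that is followed by a full cycle gives the two-cycle figures above.
- A reader might also infer that any drug left at its starting dose scores 100%. That needs every planned dose to be taken. Table 4 omits pomalidomide for the rest of a cycle in several situations, which does lower RDI. Section 7.7.1 also allows adjustments at the investigator's discretion, so clarithromycin and dexamethasone need not stay at full dose.
- Repeated delays with every drug at full dose are not a realistic picture of selinexor in haematologic delays, because Table 4 reduces it.

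The replacement also needs a convention at the end of treatment. If a final hold counts, three full cycles followed by a 29-day hold ending in removal score 84/(84 + 29) = 74.3%. The same 84 days of dosing score 100% if the permanent stop is dated at the end of cycle 3. The rule is defensible, but it has to be written down.

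**Conclusion.** The point holds as a minor one. As written, a cycle start delayed by up to 4 weeks does not itself lower RDI. Any fall comes from fewer mg taken, including a dose reduction that accompanies the delay.

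For a fully dosed drug the overstatement is 100 − 88.9 = 11.1 to 100 − 66.7 = 33.3 points over two cycles with one late start. Over ten cycles, under the assumed patterns, it is 100 − 97.6 = 2.4 to 100 − 69.0 = 31.0 points. For selinexor after a one-level reduction it is 1.7 to 6.4 points.

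These figures rest on no drug being taken during holds and on assumed delay patterns. The toxicity rates in the Background make delays foreseeable but do not say how often cycles start late, so the size of the bias in this trial cannot be predicted. A reader might infer that the trial's efficacy conclusion is weakened. It is not: no hypothesis, threshold or decision is attached to RDI, and the response-rate test, its alpha and its power are unaffected.

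**What to change.** Replace the RDI definition in 12.4.3 with:

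> For each drug, RDI = (total mg taken / actual weeks) / (that patient's planned cycle 1 dose / 4 weeks) × 100. Actual weeks run from C1D1 to day 28 of the last cycle started, or to the date study treatment is permanently stopped if that is later, and include all delays between cycles.

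Also report, per patient, the number of delayed cycle starts and the days of delay.

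Two features are deliberate.

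- The patient's own planned cycle 1 dose stays as the reference, so those who start at level -1 for renal or hepatic impairment are not penalised. Against level 0 they would score 14,000/28,000 = 50% for clarithromycin or 63/84 = 75% for pomalidomide with every dose taken on time.
- A stop within a cycle still counts 28 days. Otherwise selinexor stopped on day 16 after three doses would score (180/(16/7))/45 = 175%.

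The cost is a wording change to 12.4.3. Diaries are already collected and 7.7.1 already requires delays to be documented. No dosing rule, data collection or sample size changes.
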